8.6.4 Other Safety Evaluations

Vital signs will be summarized as appropriate

8.7 Patient Reported Outcomes

The PRO measures based on questionnaires (HIV Symptom Index and Pittsburg Sleep Quality Index, see Appendix 2) may be summarized by visit using descriptive statistics.

8.8 Sample Size

A total of approximately 100 HIV-1 infected subjects

8.9 Analysis Schedule

The Week 48 analysis will be conducted after all subjects either complete their Week 48 visit or prematurely discontinue from the study drug, respectively. Final analysis will be performed after all subjects complete the study or prematurely discontinue from the study

9. RESPONSIBILITIES

9.1 Good Clinical Practice

The rights and welfare of the individual clinical research subject must always be the paramount consideration in conducting clinical research. Accordingly, clinical research must be conducted in a manner that protects the rights, welfare and confidentiality of the human subject and also assures data credibility by protecting the integrity of accurate data that has been demonstrably collected according to the approved protocol.

9.2 Investigator Responsibilities

9.2.1 General Responsibilities

The Investigator is responsible for:

- Ensuring that the study is conducted according to the signed investigator statement/agreement, the investigational plan (study protocol), applicable regulations
- Ensuring that all persons assisting with the trial are adequately informed about the protocol, the study drug, their trial-related duties and functions
- Protection of the rights, safety, and welfare of subjects under the investigator's care
- Control of the study drug included in the investigation.
- Assuring that each subject's informed consent is obtained appropriately
- Proper delegation of authority for the conduct of various aspects of the study so that the investigator retains control and knowledge of the study

9.2.2 Control of Study Drug

The investigator shall control the study drug. The Investigator is responsible to ensure that:

- The study drug is administered only to subjects under the investigator's personal supervision or under the supervision of a qualified sub-investigator responsible to the investigator.
- The study drug is not to be supplied/provided to any person not authorized to receive it.
- Adequate records of the disposition of the study drug are maintained, including dates, quantity, receipt, distribution to subjects, and disposition.

9.2.3 Medical Decision Making

An MD/DO must be designated as responsible for all trial-related medical decisions. Medical decisions must be made by a qualified person permitted by state licensure laws to make or enact such decisions. The investigator should:

- Ensure that adequate medical care is provided to a subject for any adverse events related to the trial, during and as follow-up to a subject's participation.
- Inform a subject when medical care is needed for intercurrent illness(es) of which the investigator becomes aware.
- Inform the subject's primary physician about the subject's participation in the trial if the subject
 agrees to the primary physician being informed and has signed a HIPAA Authorization form
 permitting such disclosure.

9.2.4 IRB/IEC Review and Approval

The investigator shall assure that initial and continuing review of the proposed clinical study is performed according to the policies and procedures of the Central Institutional Review Board (IRB), as well as with any other IRB that has jurisdiction.

Continuous approval from the IRB must be maintained.

All unanticipated problems involving risk to human subjects or others are promptly reported to the IRB. All serious adverse events are reported to the IRB within twenty-four hours of time investigator is aware of the event.

Any changes in the research activity are promptly reported to the IRB.

No changes are made in the research without IRB approval, except where necessary to eliminate apparent immediate hazards to human subjects.

9.2.5 Informed Consent

The Investigator is responsible for obtaining written informed consent from each individual participating in this study after adequate explanation of the aims, methods, objectives, and potential hazards of the study and before undertaking any study related procedures. The investigator must use the most current IRB/IEC-approved consent form for documenting written informed consent. Each informed consent (or assent as applicable) will be appropriately signed and dated by the subject's legally authorized representative and the person conducting the consent discussion, and also by an impartial witness if required by IRB/IEC or local requirements. The consent form will inform subjects about sample retention.

9.2.6 Confidentiality

The investigator will assure that subjects' anonymity will be strictly maintained and that their identities are protected from unauthorized parties. All information and data will be collected by the investigator. All collected data concerning participants or their participation in this study will be considered confidential and maintained in a HIPAA-compliant electronic medical recording system. Subject data pertinent to the study will be de-identified and access limited only to personnel directly involved in this research study. All data used in the analysis and reporting of this evaluation will be used in a manner without identifiable reference to the participant. Study data will not be transmitted nor disclosed to a third-party. Paper records will be kept in secure files and electronic records will be password protected.

9.2.7 Study Files and Retention of Records

The investigator shall keep and maintain adequate and accurate records, including:

- Case histories on each individual study subject that record all observations and other data pertinent to the investigation
- Screening, enrollment, and informed consent documentation; demonstrating that informed consent was obtained prior to participation in the study
- Study reports, including reports of progress, safety, financial disclosure and final completion

9.2.7.1 Records Retention as Required

Midland Research Group, Inc. will use on-site facility and if storage becomes unavailable due to capacity of documents, then Midland Research Group, Inc., will use an offsite facility once documents are ready to be retained for retention, if applicable.

FDA regulation requires an investigator to retain records a minimum of two years after the close of the study or after the records are no longer required to support a drug or marketing application, whichever is longer. Contract commitments must be met.

9.2.7.2 Record Transfer or Record Destruction

All record transfers or record destruction will be verified and documented.

9.2.8 Case Report Forms

For each subject consented, a study file will be completed by an authorized study staff member who has completed training for this function. The study file will only capture the data required per the protocol schedule of events and procedures. The Inclusion/Exclusion Criteria and Enrollment should be completed only after all data related to eligibility have been received. Subsequent to data entry, a second staff member will perform source data verification.

9.2.9 Study Drug Accountability and Return

Unused study drug supplies will be returned to Gilead. Investigator will assist with disposal procedures and provide appropriate instruction for destruction of used study drug supplies.

9.2.10 Protocol Compliance

The Investigator is responsible for ensuring the study is conducted in accordance with the procedures and evaluations described in this protocol.

9.3 Sponsor Responsibilities

9.3.1 Protocol Modifications

Protocol modifications, except those intended to reduce immediate risk to study subjects, may be made only by the Investigator, who must submit all protocol modifications to the IRB in accordance with local requirements and receive documented IRB approval before modifications can be implemented.

9.3.2 Study Report and Publications

The Investigator is responsible for submitting any reports within time periods and according to procedures called for by:

- Midland Research Group, Inc. or applicable division or departmental policy or procedures, including the Institutional Review Board (IRB)
- Contractual agreements with collaborators, etc.

9.3.3 Payment Reporting

Investigators and their study staff may be asked to provide services performed under this protocol. If required under applicable statutory and regulatory requirements, Midland Research Group Inc. will capture and disclose to Federal and State agencies any expenses paid or reimbursed for such services, including any clinical trial payments, meal, travel expenses or reimbursements, consulting fees, and any other transfer of value.

9.3.4 Access to Information for Monitoring

As per Gilead contract

9.3.5 Access to Information for Auditing or Inspection

9.3.6 Study Discontinuation

The investigator reserves the right to terminate the study at any time. Should this be necessary, they will arrange discontinuation procedures and notify the appropriate regulatory authorities and the IRB. In terminating the study, the Investigator will assure that adequate consideration is given to the protection of the subjects' interests.

10. PUBLICATIONS

Midland Research Group, Inc. shall adhere to the *Recommendations for the Conduct, Reporting, Editing and Publication of Scholarly Work in Medical Journals* established by the International Committee of Medical Journal Editors.

APPENDIX 1. SCHEDULE OF STUDY VISITS

	SCREENING VISIT	Day 1 a	WEEK 4 ^a	WEEK 8 a	WEEK 12 ^b	WEEK 24 ^b	WEEK 36 ^b	WEEK 48 °	EARLY DISCONTINUATION
Informed Consent	X								
Patient Questionnaires		X	X		X			X	X
Height	X								
Weight	X	X	X	X	X	X	X	X	X
Vital Signs	X	X	X	X	X	X	X	X	X
Complete Medical History & Physical Exam	X								
Concomitant Medication Review	X	X	X	X	X	X	X	X	X
Assess for Adverse Experiences			X	X	X	X	X	X	X
Abbreviated History & Physical Exam		Х	Х	Х	Х	Х	Х		
Hematology	X	X	X	X	X	X	X	X	X
Chemistry	X	X	X	X	X	X	X	X	X
CD4 Profile	X	X	X	X	X	X	X	X	X
HIV- RNA Quantitative	X	X	X	X	X	X	X	X	X
Fasting Lipid Profile		X			X	Х	X	X	X
Plasma and serum Storage Sample		X	X	X	X	X	X	X	X
Urinalysis	X		X	X	X	Х	Х	X	X
Hepatitis B Surface antigen, Surface antibody, and Core Antibody ^d	X								X
Hepatitis C antibody e	Х								X
Plasma Hepatitis B viral load ^f	X		Х	Х	Х	Х	Х	Х	X
Females of childbearing potential: Pregnancy Test (Urine)	Х	X	Х	X	X	Х	Х	Х	Х
Dispensing or Administration of Study Drug		Х	Х	Х	Х	Х	Х		
Counting of Returned Study Drug			Х	X	X	Х	Х	Х	Х

a ±2 days

b ±6 days

^{±6} weeks

If Hepatitis B Surface antigen positive or if Ag/Ab negative with Core antibody positive: plasma qualitative and quantitative HBV DNA, Hepatitis B virus e-antigen and antibody

e If Hepatitis C antibody positive, HCV RNA will be performed

f If Hepatitis B coinfected

Page 29 of 38

Prolonged QTc	450-470 Or increase <30 above baseline	471-499 Or increase 30-50 above baseline	>499 Or increase >50 above baseline	Life threatening dysrhythmia
Thrombus	NA	DVT, no intervention or anticoagulation indicated	DVT, intervention or anticoagulation indicated	PE or life- threatening embolism
Vasovagal episode	No LOC	LOC	NA	NA
Ventricular dysfunction	NA	Asymptomatic and intervention indicated	New/worsening symptomatic CHF	Life threatening CHF
Bronchospasm	FEV1 70-80%	FEV1 50-69%	FEV1 25-49%	FEV1<25%, cyanosis or intubation
Dyspnea	On exertion, minimal, without impact on activities	On exertion, moderate, with impact on activities	At rest, unable to perform typical activities	Resp. failure with vent support indicated
Uveitis	Asymptomatic	Symptomatic or intervention indicated	Posterior or pan- uveitis or	Disabling visual loss

			operation indicated	
Visual changes from baseline	minimal, without impact on activities	moderate, with impact on activities	unable to perform typical activities	Disabling visual loss
Alopecia	Thinning detectable by subject	Thinning/patchy hair loss detectable by provider	Complete hair loss	NA
Rash	Localized macular rash	Diffuse rash or target lesions; no vesicles, bulla or ulceration. No mucosal involvement	Diffuse rash or target lesions; with vesicles, few bulla or superficial ulceration. mucosal involvement of one site	Extensive bullous lesions/more than one site of mucosal involvement, Stevens-Johnson syndrome or toxic epidermal necrolysis
Pigmentation changes	Slight or localized	Marked or generalized	NA	NA
pruritus	minimal, without impact on activities	moderate, with impact on activities	Severe, unable to perform typical activities	NA
Anorexia	Mild, not decreasing intake	Decreased intake, no significant weight loss	Significant weight loss	Aggressive intervention indicated (i.e. feeding tube) or life threatening
Ascites	Asymptomatic	Symptomatic, Intervention indicated	Symptomatic despite intervention	Life threatening consequences
Cholecystitis	NA	Medical intervention indicated	Procedure indicated	Life threatening consequences (sepsis/perforation)
Constipation	NA	Persistent, requiring regular use of diet modification, laxatives/enemas	Obstipation with manual evacuation indicated	Life threatening consequences (obstruction)
Diarrhea	Transient/ intermittent or increase of >3 stools over baseline/24 hr.	Persistent or increase of 4-6 stools over baseline/24 hr.	Bloody diarrhea or increase of >6 stools over baseline/24 hr.	Life threatening consequences (shock)
Dysphagia	Able to eat usual diet	Causes alteration of diet, but no medical	Causes severe alteration of diet, medical	Life threatening reduction of oral intake

		intervention indicated	intervention indicated	
Mucositis/stomatitis	Erythema	Patchy Ulcerations or pseudo- membranes	Confluent Ulcerations or pseudo- membranes or mucosal bleeding	Tissue necrosis or diffuse mucosal bleeding or life threatening consequences
Nausea	Transient or intermittent	Persistent resulting in decreased oral intake 24-48 hours	Persistent resulting in minimal oral intake >48 hours or aggressive rehydration indicated	Life threatening consequences
Pancreatitis	NA	Symptomatic, no hospitalization indicated	Symptomatic, hospitalization indicated	Life threatening consequences
Proctitis	Discomfort	Minimal interference with usual activities or medical intervention indicated	Unable to perfume usual activities or operative intervention indicated	Life threatening consequences
Vomiting	Transient or intermittent	Persistent resulting in decreased oral intake 24-48 hours	Persistent resulting in minimal oral intake >48 hours or aggressive rehydration indicated	Life threatening consequences
Psychiatric issues (i.e. anxiety, agitation, depression, mania, psychosis)	minimal, without impact on activities	moderate, with impact on activities	Severe, unable to perform typical activities	Behavior potentially harmful to self/others or unable to perform self-care
AMS	minimal, without impact on activities	lethargy, with impact on activities	Confusion, memory impairment lethargy, or somnolence, unable to perform typical activities	Delirium/obtundation or coma
Ataxia	Minimal but detectable on exam, without impact on activities	moderate, with impact on activities	marked, unable to perform typical activities	Disabling causing inability to care for self
Cognitive and behavior (including	Minimal, without impact on	moderate, with impact on	marked, unable to perform typical	Disabling causing inability to care for

dementia and ADD)	activities. No special resourced indicated	activities or part- time special resourced indicated	activities or full- time special resourced indicated	self or institutionalization
CNS Ischemia	NA	NA	Transient ischemic attach	CVA/stroke with neurological deficit
headache	Minimal but detectable on exam, without impact on activities	moderate, with impact on activities	severe, unable to perform typical activities	Disabling causing inability to care for self or hospitalization indicated
Insomnia	NA	moderate, with impact on activities or part-time special resourced indicated	marked, unable to perform typical activities or full-time special resourced indicated	Disabling causing inability to care for self
Neuromuscular Weakness	Asymptomatic but detectable on exam, without or minimal impact on activities	moderate, with impact on activities	severe, unable to perform typical activities	Disabling causing inability to care for self or respiratory failure
Sensory alteration	Asymptomatic but detectable on exam, without or minimal impact on activities	moderate, with impact on activities	severe, unable to perform typical activities	Disabling causing inability to care for self or respiratory failure
Seizure, new onset	NA	1 seizure	2-4 seizures	Prolonged or repetitive seizures or difficult to control
Seizure, pre- existing	NA	Increased frequency, no change in character	Change from baseline in either duration or quality	Prolonged or repetitive seizures or difficult to control
Syncope (not associated with a procedure)	NA	Present	NA	NA
vertigo	without impact on activities	moderate, with impact on activities	severe, unable to perform typical activities	Disabling causing inability to care for self or respiratory failure
Arthralgia	without impact on activities	moderate, with impact on activities	severe, unable to perform typical activities	Disabling causing inability to care for self or respiratory failure

Bone Mineral Loss	BMP t-score or z-score -2.5 to - 1.3	BMP t-score or z- score <-2.5	Pathological fracture	Pathological fracture causing life threatening consequences
myalgia	without impact on activities	moderate, with impact on activities	severe, unable to perform typical activities	Disabling causing inability to care for self or respiratory failure
Osteonecrosis	NA	Asymptomatic but with radiologic findings and no surgical intervention indicated	symptomatic with radiologic findings or surgical intervention indicated	Disabling bone pain with radiologic findings causing inability to care for self
Acute systemic allergic reaction	Localized urticaria with no medical intervention indicated	Localized urticaria with mild angioedema with no medical intervention indicated	Gen urticaria or angioedema with medical intervention indicated or bronchospasm	Anaphylaxis, laryngeal angioedema, laryngeal edema or life threatening bronchospasm
chills	without impact on activities	moderate, with impact on activities	severe, unable to perform typical activities	NA
Fatigue/malaise	without impact on activities	moderate, with impact on activities	severe, unable to perform typical activities	Incapacitating symptoms, unable to perform basic self-care
Fever	99.8-101.5	101.6-102.8	102.9-104.9	>104.9
pain	without impact on activities	moderate, with impact on activities	severe, unable to perform typical activities	Incapacitating symptoms, unable to perform basic self-care
Unintentional weight loss	NA	5-9% loss of body weight	10-19% loss of body weight	>19% loss of body weight or aggressive intervention indicated (feeding tube, TPN)
Lipodystrophy or lipoatrophy	detectable by subject	Detectable by provider	Obvious or disfiguring	NA
Diabetes mellitus (new onset)	NA	without indication for medications	Medications indicated	Life threatening consequences
Diabetes mellitus (existing)	NA	Requiring modification of medications	Lack of control despite medication modification	Life threatening consequences
gynecomastia	detectable by subject	Detectable by provider	Obvious or disfiguring	NA

Hyperthyroidism	asymptomatic	Symptoms causing moderate impact of activities OR medication indicated	Symptoms causing inability to perform activities OR medication indicated	Life threatening consequences
hypothyroidism	asymptomatic	Symptoms causing moderate impact of activities OR medication indicated	Symptoms causing inability to perform activities OR uncontrolled despite medication	Life threatening consequences
Intermenstrual bleeding	Spotting	≤ typical menstrual cycle	≥ typical menstrual cycle	Hemorrhage with life threatening hypotension
Urinary obstruction (i.e. stone)	NA	Without hydro- nephrosis or acute kidney injury	With hydro- nephrosis or acute kidney injury	Life threatening consequences
Infection (other than HIV)	Localized, no systemic antimicrobial treatment indicated AND symptoms causing minimal impact on activities	Systemic antimicrobial treatment indicated OR symptoms causing >minimal impact on activities	Systemic antimicrobial treatment indicated AND symptoms inability to perform activities OR operation intervention indicated (beyond simple I&D)	Life threatening consequences (i.e. septic shock)

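### Appendix 2 lets some events meet Grade 2 and Grade 3 at once, on either side of the drug-hold threshold, with no rule for choosing the grade

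*Combined protocol and SAP*

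**What the plan says.** Section 7.2.2 grades adverse event severity by Appendix 2, and Section 7.4 uses the same appendix for toxicity management. Under Section 7.4.1, Grades 1 and 2 leave continuation to the Investigator. Under Section 7.4.2, a Grade 3 event judged related to study drug (confirmed by repeat testing if it is a laboratory finding) means the drug is withheld until the event falls to Grade 2 or lower.

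The rows of Appendix 2 that matter are:

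- **Hyperthyroidism.** Grade 2: "Symptoms causing moderate impact of activities OR medication indicated". Grade 3: "Symptoms causing inability to perform activities OR medication indicated".
- **Hypothyroidism**, the next row. Its Grade 2 text is the same as for hyperthyroidism. Grade 3: "Symptoms causing inability to perform activities OR uncontrolled despite medication".
- **Diabetes mellitus (new onset).** Grade 2: "without indication for medications". Grade 3: "Medications indicated".
- **Intermenstrual bleeding.** Grade 2: "≤ typical menstrual cycle". Grade 3: "≥ typical menstrual cycle".
- **Hypernatremia.** Grade 2 is 150-154 and Grade 3 is 154-159.
- **Total bilirubin.** Grade 2 is 1.5-2.5 x ULN and Grade 3 is 2.5-5.0 x ULN.
- **Diarrhea.** The Grade 1 count is "increase of >3 stools over baseline/24 hr", Grade 2 is 4-6 and Grade 3 is more than 6.

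Section 8.6.2 plans adverse event summaries by grade. Section 8.6.3 summarizes treatment-emergent laboratory abnormalities and the maximum grade per parameter.

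**The concern.** The step from Grade 2 to Grade 3 changes the instruction from discretion to a mandatory hold. An event that meets both cells is subject to both instructions, and nothing in the plan says which prevails. Two assessors could each follow the scale and handle the same event differently.

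The restart rule has the same gap. Drug resumes once the event is at Grade 2 or lower, but a hyperthyroidism case for which medication is still indicated goes on meeting Grade 2 and Grade 3 together. The summaries in Sections 8.6.2 and 8.6.3 inherit whichever grade was recorded.

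**Working it through.** The plan gives no figure to reproduce and no event rates. The check lists which cells each case satisfies. The counts below are counts of combinations, not probabilities.

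**Hyperthyroidism, medication indicated and disease not uncontrolled.** The inputs are the hyperthyroidism cells, the hypothyroidism Grade 3 cell and the new-onset diabetes cells.

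| Symptom state | Grades met as written | Hypothyroidism wording in Grade 3 | Same, higher grade taken | Diabetes pattern, higher grade taken |
|---|---|---|---|---|
| Asymptomatic | 1, 2, 3 | 1, 2 | 2 | 3 |
| Moderate impact | 2, 3 | 2 | 2 | 3 |
| Inability | 2, 3 | 2, 3 | 3 | 3 |

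The inability state reaches Grade 3 through its own symptom clause, whichever repair is chosen. The states left open by the duplicated clause are the other two: 3 - 1 = 2 of 3. Taking the higher grade without editing the cell gives 3, 3, 3, so the sentence alone would turn every such case into a hold if drug-related.

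**Intermenstrual bleeding, relative to a typical cycle.** A lighter bleed meets Grade 2 only and a heavier one Grade 3 only. An equal bleed meets Grades 2 and 3. With Grade 3 made strictly greater, an equal bleed meets Grade 2 only.

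**Laboratory rows.** Sodium of 154 lies in 150-154 and in 154-159. Bilirubin of 2.5 x ULN lies in 1.5-2.5 and in 2.5-5.0. Each therefore meets Grades 2 and 3. Both analytes are in the chemistry profile (Section 6.2.4.1), which Appendix 1 schedules at every visit.

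**Diarrhea, non-bloody.** Grade 1 also lists transient or intermittent diarrhea, and Grade 2 also lists persistent diarrhea.

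| Pattern, increase in stools | As written (>3) | If Grade 1 were ≤3 | Higher grade, either sign |
|---|---|---|---|
| Transient, 1-3 | 1 | 1 | 1 |
| Transient, 4-6 | 1, 2 | 1, 2 | 2 |
| Transient, 7 or more | 1, 3 | 1, 3 | 3 |
| Persistent, 1-3 | 2 | 1, 2 | 2 |
| Persistent, 4-6 | 1, 2 | 2 | 2 |
| Persistent, 7 or more | 1, 2, 3 | 2, 3 | 3 |

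With either sign, 4 of 6 combinations meet more than one grade and 2 of 6 span the hold threshold. Once the higher grade is taken, all six are settled and the sign makes no difference.

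**The case against.** The strongest reply is that a severity scale is read by taking the highest grade met. Appendix 2 seems to assume this. In the infection row, systemic treatment is an alternative criterion in Grade 2 and part of a joint criterion in Grade 3, so an infection meeting that joint criterion meets both grades. On that reading nothing is undetermined, and a tie is held, which is the cautious outcome. This is a fair account of how the table is probably used, but the rule is not written down. Applied to hyperthyroidism as it stands, it also leaves the Grade 2 medication clause unable ever to decide a grade, so that row still needs repair.

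A second reply is that clinicians resolve such cases. Section 7.2 gives severity assessment to the investigator or a qualified sub-investigator, and Section 7.4 sends toxicity questions to the Investigator. That settles single cases but does not remove the conflicting instructions. The clinical-severity sentence in Section 7.2.2 covers only adverse events associated with laboratory abnormalities. The maximum grade in Section 8.6.3 is a laboratory summary over time and does not choose between two cells for one result.

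Three points on practical reach stand. No thyroid test is scheduled in Section 6.2.4.1 or Appendix 1. The bleeding overlap is a single point on a quantity the plan does not measure. The hold applies only to Grade 3 events judged drug-related.

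A reader might also infer more than the text supports:

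- *All medicated hyperthyroidism cases are undetermined.* The inability state is Grade 3 under any repair.
- *The intended wording cannot be known.* Hypothyroidism matches hyperthyroidism in Grades 1, 2 and 4 and in the first Grade 3 clause, which points clearly to its second clause. The diabetes row is built differently and has no symptom criteria.
- *The diarrhea sign changes dosing.* The table above shows that it changes no grade once the higher grade is taken. The character may also differ in the source PDF.

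**Conclusion.** The point holds as a minor drafting defect in a rule that governs dosing. Hyperthyroidism has no fixed grade in two of its three medicated states. Intermenstrual bleeding, sodium and bilirubin each overlap at one value. No tie rule is stated.

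The consequence is a few possible drug holds and some movement in the adverse-event and laboratory summaries by grade. How many subjects this would touch cannot be estimated, because the documents give no event rates. The primary endpoint is classified from HIV-1 RNA by the snapshot algorithm, which does not use adverse event grade, so I see no effect on it.

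The conclusion rests on the Appendix 2 cells having been read correctly from the PDF. The choice of repair for hyperthyroidism rests on the parallel with hypothyroidism. That parallel is strong but is still an inference, so the medical lead should confirm it.

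**What to change.** Make these changes together:

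1. Change hyperthyroidism Grade 3 to "Symptoms causing inability to perform activities OR uncontrolled despite medication", matching the adjacent hypothyroidism row, once the medical lead confirms.
2. Change intermenstrual bleeding Grade 3 to strictly greater than a typical menstrual cycle.
3. Add one sentence at the head of Appendix 2: *any clinical or laboratory event that meets the criteria of two grades is assigned the higher grade.* This also settles sodium at 154, bilirubin at 2.5 x ULN and the diarrhea overlaps.

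The first change must not lag behind the third, because the sentence alone would make every medicated hyperthyroidism case at least Grade 3 without anyone having decided so. The diarrhea Grade 1 sign needs only an editorial check against the source.

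The cost is two table cells and one sentence, carried in the next IRB-approved amendment. The small downside is that remaining ties, if drug-related, go to a hold rather than to discretion.
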